6.4.6 RT Planning and Radiation Treatment

The technique for delivering the external beam treatment will be employed per institutional standard guidelines. Identical treatment planning studies will be performed both before (pre-TraceIT) and after (post-TraceIT) hydrogel injection in each subject. The technique and setup for these two simulation studies should be nearly identical particularly with respect to patient immobilization and respiratory motion management (i.e., active breath-hold method, forced shallow breathing with abdominal compression or real-time tracking and/or gating) and beam arrangement and angle. Planning set-up/parameters for the pre- and Post-injection RT planning will be documented within the CRF.

The initial **minimum target dose** will be 33 Gy in 5 fractions (6.6 Gy per fraction) or an equivalent biologically effective dose if >5 fractions is being delivered. The goal should be that at that the V33Gy for the PTV be at least 95%. CT simulation will be performed with immobilization when possible.

Normal tissue contours will be performed in accordance with the Upper Abdominal Normal Organ Contouring Guidelines recommended by the 2013 RTOG Consensus Panel.

Target dose constraints for OAR include:

Organs at Risk (OAR)	Dose Constraint*
Proximal duodenum, proximal stomach and small bowel	V15Gy<9cc, V20Gy<3 cc, and V35Gy<1cc A duodenal maximum dose of \leq 32 Gy should initially be attempted
Stomach	V12Gy<50% and V35Gy<1cc
Liver	V12Gy<50%
Combined Kidneys	V12Gy<75%;
Spinal Cord	V8Gy<1 cc

*or biologically equivalent dose constraints for >5 fractions

Target coverage, doses to OAR, dose conformity, mean and maximum proximal duodenal dose and dose volume histograms will be documented pre- and post-TraceIT Injection.

6.4.7 Follow-up for Non-Injection Subjects (30 days +7 days or until resolution/stabilization of an adverse event if applicable)

A “Non-Injection” Subject is a subject who was intended to be treated with TraceIT, but in whom TraceIT was unable to be injected. No further image collection is required for these subjects.

- 30 Day Visit to include:
 - Physical assessment: including sitting blood pressure, pulse, temperature and Zubrod Performance Score
 - Assessment of Intestinal Adverse Events documented using CTCAE criteria
 - Other Adverse Events per NCI CTCAE
 - Changes in concomitant medications used to treat intestinal symptoms

6.4.8 Post-injection RT Planning (less than 28 days following Index Procedure)

The following assessments will be performed during the post-injection RT planning:

- Repeat CT Planning Imaging using the same number of beams and set-up as Pre-injection planning
- Dosimetric data to be collected include: V5 (volume (cc) of the duodenum receiving 5 Gy or more), V10, V15, V20, V25, V30, V35, V40, duodenal mean/maximum doses, GTV/PTV minimum/mean/maximum doses as well as GTV/PTV volume, and total duodenal volume.
- Theoretical dose escalation (maximum dose to GTV while maintaining duodenal dose constraints)
- TraceIT Hydrogel and Fiducial Visibility Scoring: Visibility of the TraceIT hydrogel and the fiducial markers will be scored as follows: 1 – not visualized; 2 – faint or trace visibility (shadow or haze); 3 – visibility but indistinct borders (definable entity, not just haze); 4 – partially distinct border, partial haze; and 5 – clearly visualized, unequivocal.

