Initial RT Planning & Documentation	
Subjects who appear to meet the inclusion criteria and do not present with any of the exclusion criteria will undergo a CT for baseline RT Planning.
 
The initial minimum target dose will be 33 Gy in 5 fractions (or an equivalent biologically effective dose if >5 fractions is being delivered). CT simulation will be performed with immobilization.
 
Target dose constraints for OAR include:
 
  
 Organs at Risk (OAR)	Dose Constraint*	
   
 Proximal duodenum, proximal stomach and small bowel	V15Gy<9cc, V20Gy<3 cc, and V35Gy<1cc A duodenal maximum dose of \leq32 Gy should initially be attempted	
 
 Stomach	V12Gy<50%, V35Gy<1cc	
 
 Liver	V12Gy<50%	
 
 Combined Kidneys	V12Gy<75%;	
 
 Spinal Cord	V8Gy<1 cc	
  
 
*or biologically equivalent dose constraints for >5 fractions
 
Radiographic tumor-vessel interface will be documented.
 
Other dosimetric data to be collected include: V5 (volume (cc) of the duodenum receiving 5 Gy or more), V10, V15, V20, V25, V30, V35, V40, duodenal mean/maximum doses, GTV/PTV minimum/mean/maximum doses as well as GTV/PTV volume, and total duodenal volume.
	Organs at Risk (OAR)	Dose Constraint*	Proximal duodenum, proximal stomach and small bowel	V15Gy<9cc, V20Gy<3 cc, and V35Gy<1cc A duodenal maximum dose of \leq 32 Gy should initially be attempted	Stomach	V12Gy<50%, V35Gy<1cc	Liver	V12Gy<50%	Combined Kidneys	V12Gy<75%;	Spinal Cord	V8Gy<1 cc
Organs at Risk (OAR)	Dose Constraint*												
Proximal duodenum, proximal stomach and small bowel	V15Gy<9cc, V20Gy<3 cc, and V35Gy<1cc A duodenal maximum dose of \leq 32 Gy should initially be attempted												
Stomach	V12Gy<50%, V35Gy<1cc												
Liver	V12Gy<50%												
Combined Kidneys	V12Gy<75%;												
Spinal Cord	V8Gy<1 cc												

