As radiation dose from stereotactic radiation drops off very quickly, displacement of the duodenum from the pancreas by only a few millimeters would be expected to significantly diminish duodenal toxicity. A similar product, SpaceOAR, was cleared by the FDA in 2015 specifically for use to temporarily position the anterior rectal wall away from the prostate during radiotherapy for prostate cancer. In a prospective randomized (2:1), controlled multicenter study evaluating 222 men with clinical stage T1 or T2 prostate cancer, SpaceOAR use was associated with significant rectal dosimetric benefits and reduced rectal toxicity severity as well as a decrease in the proportion of patients experiencing declines in bowel quality of life.^{18,19} Thus it is believed, that incorporation of application of the TraceIT Tissue Spacer into the regimen of radiotherapy treatment can allow for improvement in RT delivery in multiple aspects including: 1) allowing for safe duodenal dose constraints to be achieved at the target prescription dose; 2) allow for an increase in tumor volume coverage while maintaining acceptable duodenal dose constraints or 3) allow for an individualized dose escalation prescription while maintaining acceptable duodenal dose constraints. Space creation between the duodenum and HOP may also provide a benefit in reducing incidental radiation to the duodenum due to intra and interfraction motion.

Success in any one of the parameters noted above would make TraceIT Tissue Spacer an important tool for the radiation oncologist as they plan and treat patients with cancer of the pancreatic head.

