7.6.3 Radiotherapy Benefits

Treatment planning will be performed as a component of the Baseline Assessment and repeated following TraceIT administration. For both scans, summary descriptive statistics will be presented by assessment (i.e., Pre vs. Post TraceIT Administration) for all target volume and dose constraint measurements. For the post-TraceIT procedure data, the relative reduction from baseline in dose (V15, V20, V35, mean and maximum duodenal dose, etc.) to the duodenum will also be calculated and summarized. For continuous variables, the paired sample t-test will be used to test for a difference in means between treatment plans.

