3.3 Exploratory Effectiveness Endpoint

The exploratory effectiveness endpoints are defined as:

- Incidence of resection
- Histology of duodenal tissues when resection is performed
- Incidence of acute (within 3 months) and late (>3 months) duodenal toxicity (for unresected subjects)
- Theoretical dose escalation from post-TraceIT treatment plan
- TraceIT persistence (at 6-months post-TraceIT in nonresected subjects)
- Change from baseline in EORTC QoL (QLQ-C30) and QLQ-PAN26
- Comparability of visualization of the fiducial marker and TraceIT hydrogel using a standardized visualization score
- Progression free and overall survival through follow-up

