3.3.1 Statistical Methods

The proportion of resected subjects in the MITT or PP population, localized (resectable, BRPC or LAPC) subgroup may be calculated with an exact (Clopper-Pearson) 95% confidence interval for the true proportion, when appropriate.

The incidence of acute (within 3 months) and late (>3 months) duodenal toxicity for unresected subjects will be reported by CTCAE grade and timing.

Histology of duodenal tissue (Duodenum Damage Score) will be summarized for those subjects when resection is performed.

The summary of theoretical dose escalation from post-TraceIT treatment plan, and , migration and stability at 2-6 weeks post-TraceIT, TraceIT persistence at 6-months post-TraceIT in non-resected subjects will be presented in separated table. The pre-TraceIT and post-TraceIT duodenal space measured by site during index procedure and/or by independent assessors will be summarized separately. Average duodenal space will be

calculated if the measurements were taken from multiple observation points or duplication.

The EORTC QLQ-C30 is a questionnaire developed to assess the quality of life of cancer patients. The pancreatic cancer module QLQ-PAN26 is intended for patients at all disease stages undergoing surgical resection, palliative surgical intervention, endoscopic palliation or palliative chemotherapy. Changes in Quality of Life Measures as assessed overall and subdomains (scales) of the EORTC-QLQ-C30 and QLQ-PAN26 will be evaluated.

The five functional scales (physical, role, emotional, cognitive and social), three symptom scales (fatigue, nausea & vomiting and pain), a global health status/QOL scale, and six single items (dyspnea, insomnia, appetite loss, constipation, diarrhea and financial difficulties) from EORTC-QLQ-C30 will be summarized according EORTC QLQ-C30 Scoring Manual third edition.

The fifteen symptom items and two functional scales from QLQ-PAN26 will be analyzed according EORTC QLQ-PAN26 Scoring Manual 2.2.

Those analysis will be repeated by localized (resectable, BRPC and LAPC), as well as resected and unresected subgroup, if applicable. Scores will be compared to baseline using either a paired t-test or Wilcoxon Signed-Rank test when appropriate.

The result of comparability of visualization of the fiducial marker and TraceIT hydrogel will be summarized using a standardized visualization score for all subjects injected with TraceIT Tissue Spacer.

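### Theoretical dose escalation is planned only on the post-TraceIT plan, so this exploratory measure does not by itself show how much escalation room goes with the spacer

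*Protocol*

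**What the plan says.** The protocol's Introduction gives three ways in which the spacer might improve radiotherapy. The third is that it may "allow for an individualized dose escalation prescription while maintaining acceptable duodenal dose constraints". SAP section 2 repeats this.

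The measure for that idea is defined in Protocol 6.4.8, under post-injection planning, as "Theoretical dose escalation (maximum dose to GTV while maintaining duodenal dose constraints". The post-injection row of the Protocol Summary has the same item. SAP 3.3 names the endpoint as "Theoretical dose escalation from post-TraceIT treatment plan", and Protocol 6.1.3 describes it the same way. The analysis in SAP 3.3.1 is "The summary of theoretical dose escalation from post-TraceIT treatment plan", presented in a table. No change or paired analysis is named for it.

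The baseline row of the Protocol Summary (Initial RT Planning & Documentation) begins "Other dosimetric data to be collected include: V5 (volume (cc) of the duodenum receiving 5 Gy or more", runs through the other dose-volume points, and closes with "GTV/PTV minimum/mean/maximum doses as well as GTV/PTV volume, and total duodenal volume". Theoretical dose escalation is not on that list.

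Other dosimetry is held for both plans. Protocol 6.4.6 states: "Target coverage, doses to OAR, dose conformity, mean and maximum proximal duodenal dose and dose volume histograms will be documented pre- and post-TraceIT Injection". Protocol 7.6.3 and SAP 3.2.1 give descriptive statistics by assessment, pre versus post, "for all target volume and dose constraint measurements", plus relative reductions in duodenal dose.

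**The concern.** The study has one arm, so each subject's baseline plan is the only comparator. The formal radiotherapy-benefit components (duodenal constraints, target coverage, duodenal dose) are all compared before and after injection. Escalation is the exception, although the Introduction offers it as a benefit of the spacer and every subject has a baseline plan made with closely matched set-up.

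A maximum attainable dose on the post-TraceIT plan depends on the subject's anatomy as well as on the space created. Some subjects may have had room to escalate before injection. Others may not have been able to meet the duodenal constraints even at the target dose. A reader who takes the post-only figure as the spacer's effect could be misled upwards or downwards. At stake is how useful this one exploratory result is for planning a later study.

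**Working it through.** No figure in either document bears on this point. The sample size of six has no effect size, standard deviation, alpha or power behind it, so there is nothing to reproduce. The check is a comparison of the data lists, followed by arithmetic on assumed values.

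**1. What is collected and compared**

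| Item | Baseline plan | Post-TraceIT plan | Pre/post comparison planned |
|---|---|---|---|
| V5 to V40, duodenal mean and maximum | yes | yes | yes |
| GTV/PTV doses and volumes | yes | yes | yes |
| Dose volume histograms, target coverage | yes | yes | documented for both |
| Theoretical dose escalation | no | yes | no |

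The GTV maximum recorded at baseline does not fill the gap. It is the maximum in a plan built for the target dose, not the highest dose attainable within the duodenal constraints.

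**2. What the post-only value leaves open**

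- Room shown by the plan = post maximum − 33 Gy (the minimum target dose in 5 fractions, Protocol 6.4.6).
- Change from pre to post = post maximum − baseline maximum.

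Assume a post maximum of 40 Gy, so the room shown is 40 − 33 = 7 Gy. The baseline maxima are also assumed.

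| Baseline maximum (Gy) | Change from pre to post (Gy) | Change as share of the 7 Gy shown |
|---|---|---|
| 28 | 40 − 28 = 12 | 171% |
| 33 | 40 − 33 = 7 | 100% |
| 36 | 40 − 36 = 4 | 57% |
| 40 | 40 − 40 = 0 | 0% |

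The escalation summary is the same in all four rows. The first row shows understatement; the last two show overstatement.

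**3. How far the planned pre/post metrics help**

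Two invented baseline duodenal histograms for a 33 Gy plan were scaled linearly until V15 < 9 cc, V20 < 3 cc or V35 < 1 cc was about to fail. The initial 32 Gy duodenal maximum was left out.

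- Metrics inside the limits (V15 = 6, V20 = 2, V35 = 0.1 cc): factor 1.066, giving 33 × 1.066 = 35.2 Gy.
- Metrics outside the V15 and V20 limits (V15 = 11, V20 = 5, V35 = 0.4 cc): factor 0.833, giving 33 × 0.833 = 27.5 Gy.

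The paired metrics therefore indicate the direction of baseline room and allow a rough figure. Scaling a fixed plan is not re-optimising it, however, and neither document plans either step.

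**4. What a paired value would deliver**

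95% CI half-width for the mean difference, in SDs of the difference = t(0.975, n − 1)/√n. The smallest possible two-sided exact signed-rank p = 2/2ⁿ.

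| Pairs | Half-width | Smallest p |
|---|---|---|
| 6 | 2.571/√6 = 1.05 SD | 0.031 |
| 5 | 2.776/√5 = 1.24 SD | 0.063 |
| 4 | 3.182/√4 = 1.59 SD | 0.125 |

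The rows for 5 and 4 pairs matter because the MITT population excludes technical failures. The estimate would be imprecise, which is why a per-subject listing is the main output.

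**The case against.** The strongest reply is that the study already holds paired evidence on this question. Duodenal metrics are reported for both plans against the same constraint table. A subject with ample baseline room would usually sit well inside the limits, and a subject with none would sit at or beyond them. The baseline plans and histograms are kept, so a baseline maximum could be derived later. This stands. It rules out a stronger inference that a reader might draw: that the study cannot tell whether escalation room comes with the spacer, or that one of the three stated benefits is unanswerable. The evidence is indirect, though, and the later derivation is unplanned and would be done with post-injection results known.

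Second, the three benefits are background rationale. Escalation is additional data collection in the protocol and exploratory in the SAP, in a study without formal hypotheses. This also stands, and it limits the importance of the point. It does not explain why the item lacks a baseline value when its neighbours have one.

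Third, Protocol 7.2 and 7.6.5 might be read as applying change-from-baseline methods to every dosimetric measure. They cannot do so for a measure with no baseline value.

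Fourth, a reader might infer that the post-only figure credits all the room to the spacer, so that the true share lies between 0% and 100%. Neither document plans such an attribution, and the range is wrong: where baseline room is negative, the share exceeds 100%.

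Finally, pairing does not isolate the spacer. If the baseline scan falls in the 45-day screening window and replanning takes place up to 28 days after the procedure, the scans could be almost 45 + 28 = 73 days apart. Planning is also open-label. This stands and belongs in the fix.

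**Conclusion.** The point holds in a limited form. Theoretical dose escalation is collected and summarised only on the post-TraceIT plan, and the planned pre/post comparisons do not cover it. By itself it does not show how much escalation room is associated with the spacer. The error can go in either direction: in the illustration, 7 Gy of visible room fits a change of anything from 0 to 12 Gy. Those gray values are assumed, since the documents give none, and they presuppose the five-fraction schedule on both plans. That the baseline value is absent rests on the documents alone.

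The consequence is modest, because the measure is exploratory, the study has six subjects, and the paired duodenal metrics give partial evidence. The change is still worth making: it turns an uncontrolled value into a within-subject comparison at little cost.

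**What to change.** - **Protocol Summary (Initial RT Planning) and 6.4.6:** add theoretical dose escalation to the baseline items. Calculate it with the same duodenal constraints, target coverage requirement and fractionation as the post-injection calculation. State the coverage requirement explicitly, because the definition in 6.4.8 mentions only the duodenal constraints.
- **SAP 3.3 and 3.3.1:** list the baseline and post-TraceIT values for each subject and summarise the within-subject difference (post minus pre) descriptively. Add a sentence that anatomical change between scans and unblinded planning limit attribution to the spacer.

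The cost is planner time for about six extra optimisations on existing CTs, one CRF field and a short SAP edit. No scan, visit or subject is added, and delivered treatment does not change.

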6.4.9 RT Initiation

RT must be initiated NLT 28 days following TraceIT administration. RT should be initiated NST 1 week from last chemotherapy dose. At the initiation of each fraction, the appearance of the TraceIT hydrogel with respect to presence and material distribution should be compared to RT planning CT.

6.4.10 Final RT Fraction

The following assessments are to be performed at the final RT fraction:

- Physical Assessment (including vital signs, weight and Zubrod performance score)
- EORTC-QLQ-C30 and QLQ-PAN26
- Assessment of duodenal focused Adverse Events documented using NCI CTCAE
- Other Adverse Events per NCI CTCAE
- Changes in concomitant medications used to treat intestinal symptoms

6.4.11 Week 2-6 Following Completion of RT (Restaging & Evaluation for Potential Resection)

The following assessments are to be performed at week 2-6 following completion of RT (Restaging and Evaluation for Potential Resection). These assessments can be performed at the time the subject returns for the restaging CT:

- Physical Examination: including sitting blood pressure, pulse, temperature, weight, anticoagulation status, Zubrod Performance Score.
- CT for restaging (also will evaluate TraceIT Persistence)
- Assessment of duodenal focused Adverse Events documented using NCI CTCAE
- Other Adverse Events per NCI CTCAE
- Changes in concomitant medications used to treat intestinal symptoms
- CA-19-9 level
- Pancreaticoduodenectomy should be targeted to be performed within 8 weeks after the completion of RT if applicable.

Restaging and determination of resectability will be performed in accordance with the standard institutional practices.

CT's will be reviewed by a radiologist and any radiological findings suggestive of duodenal injury shall be documented and graded when possible. Duodenal perforation would be suspected if there is a retroperitoneal collection of extraluminal gas or a lack of continuity of the duodenal wall. Duodenal erosion/ulceration is suspected with edema or hematoma of the duodenal wall, intramural gas accumulations, and focal duodenal wall thickening (>4 mm) as findings of small bowel injury.

6.4.12 Resected Subjects (at time of resection)

The following assessments are to be performed at time of resection:

- Physical Examination: including sitting blood pressure, pulse, temperature, weight, anticoagulation status, Zubrod Performance Score.
- Assessment of duodenal focused Adverse Events documented using NCI CTCAE if available
- Other Adverse Events per NCI CTCAE if available
- Changes in concomitant medications used to treat intestinal symptoms

6.4.13 Resected Subjects (Histopathology record)

The following assessments are to be performed at time of histopathology:

- Incidence of complete or partial response (Path PR and Path CR)
- Pathologic duodenal damage score rated by a local board-certified gastrointestinal surgical pathologist using the methods outlined by Verma et al.,¹ where:
 - 1=no/minimal signs of mucosal damage: villi remain long and slender, epithelial cells have abundant eosinophilic cytoplasm with few mitotic figures, and the lamina propria have normal amounts of inflammatory cells including few or no neutrophils.
 - 2=moderate damage where villi are blunted or absent, epithelial cells have reactive/reparative, changes with basophilic cytoplasm, increase mitotic figures, and/or small erosions or focal ulcerations; the lamina propria show increased inflammation including eosinophils and neutrophils.
 - 3=severe damage with diffuse epithelial damage absent with or without extensive ulcerations and residual surviving epithelium displaying marked reactive/reparative changes; lamina propria replaced with granulation tissue and/or overlying fibrinoid inflammatory exudates with numerous neutrophils or marked damage.

6.4.14 Additional Follow-up at Month 3 (\pm 14 days) and Month 6 (\pm 14 days) Post-Index Procedure

The following assessments will be performed at the 3 and 6 Month Post-Index Procedure visit:

- Physical Examination: including sitting blood pressure, pulse, temperature, weight, anticoagulation status, Zubrod Performance Score.
- Unresected subjects only: MRI at Month 6 post-index procedure
- Assessment of duodenal focused Adverse Events documented using NCI CTCAE
- Other Adverse Events per NCI CTCAE
- EORTC-QLQ-C30 and QLQ-PAN26
- Changes in concomitant medications used to treat intestinal symptoms
- Post-surgical complications in resected subjects

6.4.15 Long Term Follow-Up (Month 12 \pm 28 days and Month 18 \pm 28 days)

The following assessments will be performed at the 12- and 18-Month Post-Index Procedure visit:

- Physical Examination: including sitting blood pressure, pulse, temperature, weight, anticoagulation status, Zubrod Performance Score.
- Assessment of duodenal focused Adverse Events documented using NCI CTCAE
- Other Adverse Events per NCI CTCAE
- EORTC-QLQ-C30 and QLQ-PAN26
- Changes in concomitant medications used to treat intestinal symptoms

